5 STATISTICAL ANALYSIS PLAN

Efficacy analyses will be based on a modified intent-to-treat population including all subjects randomly assigned and having received at least one dose of study drug. The distribution of the primary efficacy end point time of first BM will be estimated via the Kaplan-Meier product-limit method and compared between treatment groups using the log-rank test. Secondary efficacy end points will be evaluated at the $\alpha = 0.05$ level of significance without adjustment for multiple comparisons.

This study will attempt to identify not just relevant demographic and clinical risk factors for POI following spinal fusion, but also will quantify peri-operative opioid use in this patient population in order to determine whether an increased use of opioids increases the risk of POI.

Finally, safety will be assessed by monitoring adverse events (AEs), concomitant medications, vital signs, physical examination findings, ECG findings, and laboratory test results. Withdrawals owing to AEs will be evaluated as a safety end point. Treatment-emergent AEs, potentially clinically important laboratory measurements, and premature study discontinuations will be compared between groups by use of the Fisher exact probability test.

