2.2 Drug Background

Early clinical studies evaluated the effectiveness of MNTX in treating opioid-induced constipation (OIC). Several clinical trials confirmed that MNTX was well tolerated and counteracted the GI effects of opioids, thereby enhancing gut motility without inhibiting their analgesic properties [8-10]. Only two studies to date have evaluated the potential effectiveness of MNTX in reducing the incidence of POI following GI surgery [11, 12]. Both studies were unfortunately hampered by serious design flaws. Most importantly, neither study included pre-operative administration of MNTX, which was a characteristic of the alvimopan studies that showed clinical benefit [13-15]. As such, MNTX remains at this time approved only for chronic OIC based on two double-blind, randomized, placebo-controlled trials conducted in patients with advanced illness wherein MNTX rapidly induced laxation as compared to placebo [16, 17].

In 2001, alvimopan, a related peripherally acting μ -opioid receptor (PAM-OR) antagonist that selectively targets GI μ -opioid receptors, was noted to significantly reduce the time to first flatus passage, time to first bowel movement (BM), and time to discharge in a cohort of 78 patients undergoing either partial colectomy or total hysterectomy [18]. Wolff and colleagues found similar results in a larger cohort of 469 patients undergoing bowel resection or hysterectomy [19]. These results led to approval by the FDA in 2008 of alvimopan as the first (and still only) drug for POI treatment after partial small or large bowel surgery. Unfortunately, however, alvimopan is contraindicated in patients that have taken opioids the week prior to surgery, which significantly limits its application to spinal surgery patients who are often taking opioid analgesics at relatively large doses.

As such, there is a glaring paucity of clinical evidence regarding the potential benefits of PAM-OR antagonists for POI prophylaxis. Specifically, no studies have been undertaken to date evaluating MNTX in relation to POI prophylaxis after spinal fusion. A critical clinical need therefore needs to be addressed for spinal surgery patients who suffer from POI and its associated complications and costs.

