3.2 Primary / Secondary Outcomes

The primary outcome will be the time from the end of surgery to the first bowel movement (BM; in hours). A sample size of 43 randomly assigned patients per study group (86 subjects in total) was calculated to detect a treatment effect of MNTX (90% power; alpha = 0.05). This calculation was performed with the assumption that subjects who experience their first BM by day three comprise 50% in the placebo group and 85% in the treatment group. A 10% lost-to-follow up rate was also included in the calculation. The secondary outcomes will be the time to discharge and the time to discharge eligibility (in hours). Finally, exploratory outcomes will include the amount of daily narcotics (in morphine milli-equivalents) administered during the first 4 days or up to hospital discharge. Administration of drug/placebo will be stopped should the patient experience frequent stools, defined as greater than 3 BMs per day.

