4.3 Perioperative and Postoperative Management

Enrolled patients will be given MNTX (0.15 mg/kg rounded to 8 mg or 12 mg) or placebo prior to surgery in the pre-operative holding area and every 24 hours for 3 days following surgery (a total of 4 doses). This dosing matches the FDA approved dosing for the use of MNTX in patients effected by opioid induced constipation.

Following surgery patients' BMs will be closely monitored and the time to first BM will be recorded in hours. Patients will receive routine post-operative orders including early mobilization with a physical therapist on the first post-operative morning, intravenous patient controlled anesthesia for 1-2 days transitioned thereafter to an oral opioid regimen, as well as a bowel routine comprising Docusate Sodium, Senna Glycoside, Polyethylene Glycol 3350, and Bisacodyl

suppositories (started on post-operative day 2, if needed). All patients are also routinely discharged on a tapering oral opioid regimen.

Administration of drug/placebo will be stopped should the patient experience frequent stools, defined as greater than 3 BMs per day. If a treating physician chooses to prescribe the off-label use of Methylnaltrexone for the management of post-operative ileus, the subject will be unenrolled from the study. Abdominal X-rays and CT will be collected and analyzed only if performed as standard of care to evaluate the GI tract following surgery. Additional review of concomitant medications, patient-reported pain levels (NRS), and adverse/serious adverse events will be reviewed daily for up to 96 hours following surgery and at 30 days post-operatively.

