4.7 Success Criteria

4.7.1 Primary Measure of Effectiveness

A subject will be considered a success if a BM is achieved within 3 days of surgery. The primary outcome measure of effectiveness will be determined by the comparative rate of patients achieving BM and evading POI in the MNTX group versus placebo.

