4.7.3 Tertiary Measure of Effectiveness

Tertiary measures of effectiveness will include the effect of MNTX on the amount of daily narcotics administered (in milli-equivalents) during the first 4 post-operative days or up to hospital discharge.

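### Does the exploratory opioid–ileus question in Section 5 need an arm-specific model and a rule that opioid exposure precede the first bowel movement?

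*Combined protocol and SAP*

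**What the plan says.** Section 5 first sets out the efficacy analyses, on a "modified intent-to-treat population including all subjects randomly assigned and having received at least one dose of study drug", with Kaplan-Meier curves and a log-rank test for time to first bowel movement (BM). A separate paragraph then describes a risk-factor aim. The study will try to identify "relevant demographic and clinical risk factors for POI following spinal fusion", and it "will quantify peri-operative opioid use in this patient population in order to determine whether an increased use of opioids increases the risk of POI". Nothing more is written for that aim: no model, no arm term, no exposure window and no statement on whether the arms are combined.

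Other sections bear on it:

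- Section 2.2 reports from earlier trials that "MNTX was well tolerated and counteracted the GI effects of opioids, thereby enhancing gut motility".
- Section 3.2 sizes the trial on the assumption that "subjects who experience their first BM by day three comprise 50% in the placebo group and 85% in the treatment group".
- Section 4.7.1 counts a BM within 3 days of surgery as success and speaks of the "comparative rate of patients achieving BM and evading POI in the MNTX group versus placebo". This is the nearest the documents come to defining POI.
- Section 4.7.3 makes the "amount of daily narcotics administered (in milli-equivalents) during the first 4 post-operative days or up to hospital discharge" a tertiary measure, as an outcome compared between arms.
- Section 4.3 has time to first BM recorded in hours and says that concomitant medications "will be reviewed daily for up to 96 hours following surgery and at 30 days post-operatively".

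**The concern.** The study drug is meant to interrupt the relation that this aim wants to measure. If MNTX blocks the action of opioids on the gut, more opioid should delay the first BM under placebo and do so less, or not at all, under MNTX. One coefficient over both arms then averages an unblocked and a blocked relation. Adding arm as a main effect does not separate them, because it shifts the baseline and leaves a single slope. A weak overall association might be reported as opioids mattering little after lumbar fusion, when the trial itself had removed the relation in half its subjects.

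The second worry is timing. Opioid recording over four days, or to discharge, can run past the first BM and past the 3-day success window. If subjects without a BM stay longer, they accumulate more opioid because they stayed, and the association would run backwards.

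**Working it through.** **The plan's own figure.** No figure is given for this aim. The only design figure, 43 per group, sizes the treatment comparison. The stated rates imply a hazard ratio (HR) of ln 0.15 / ln 0.50 = 2.737. Freedman's formula (two-sided 0.05, 90% power) gives 49 events. Then 49 / 0.675 = 72.6 subjects, or 37 per arm, and 37 / 0.9 = 41.1, rounded up to 42. That is close to 43, and it says nothing about opioids.

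**What is written and what is inferred.** Pooling is an inference from the reference to this patient population. The phrase reads naturally as spinal-fusion patients, and the all-dosed set is defined for efficacy analyses only. The 50% and 85% rates describe a main effect of treatment. They can hold with no opioid-by-arm interaction at all, so they do not imply a difference in slopes.

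**Size of the dilution.** Assumptions, none from the documents: placebo HR 0.60 per SD of log dose, and MNTX log HR equal to (1 − f) times the placebo value, where f is the blockade. Take 39 per arm (43 × 0.9 = 38.7), dose in the first 24 h, subjects without a BM by 24 h, and follow-up to 96 h. With Weibull BM times (shape 1.5) matched to the stated rates, simulation gives about 45 first BMs, 20 of them under placebo.

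A single Cox coefficient weights the arms roughly by events:

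- placebo share w = 20/45 = 0.44
- ratio of pooled to placebo log HR = 1 − f(1 − w)
- pooled HR = 0.60 raised to that ratio
- power ≈ Φ(|log HR| × √events − 1.96), with 45 events pooled and 20 for placebo; |ln 0.60| = 0.511

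| Blockade f | Ratio | Pooled HR | Power, pooled | Power, placebo-arm |
|---|---|---|---|---|
| 1 | 0.44 | 0.80 | Φ(0.227 × 6.71 − 1.96) = 33% | Φ(0.511 × 4.47 − 1.96) = 63% |
| 0.5 | 0.72 | 0.69 | Φ(0.369 × 6.71 − 1.96) = 70% | 63% |
| 0 | 1 | 0.60 | Φ(0.511 × 6.71 − 1.96) = 93% | 63% |

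Simulation of the same set-up (300 trials per setting) gives the same ordering. Power, pooled against placebo-arm, is 26–39% against 51–75% at full blockade, 53–76% against 45–67% at half, and 69–93% against 42–71% at none. The pooled HR is 0.78–0.80 at full blockade and about 0.66–0.70 at half.

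**Break-even.** The two powers are equal when (1 − f(1 − w)) × √45 = √20, that is f = 1/(1 + √w) = 1/(1 + 0.667) = 0.60. For w from 0.38 to 0.50 this runs from 0.62 to 0.59.

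**Precision of the alternative.** The HR detectable with 80% power in the placebo arm is exp(−2.80/√events): 0.47 with 14 events, 0.53 with 20 and 0.58 with 27.

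**Timing.** With opioid dose simulated as unrelated to BM, the first-24-h dose gave a false association in 4.3–5.5% of trials and the dose by in-hospital day in 3.4–6.3%, close to the nominal 5%. A total run to discharge (capped at 96 h) gave about 100%, 98% and 58% when discharge was assumed to follow BM by 12, 24 and 48 h. With no link between discharge and BM, a total to discharge gave 4–6%. The plan records narcotics by day and does not name such a total.

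**The case for a change.** The best case for a change is that the silence is real and cheap to fill. The plan's own rationale makes a smaller opioid slope under MNTX plausible. An analyst could fit one slope without thinking, and at full blockade an HR of 0.60 would then be reported as about 0.80. A logistic model for no BM by 72 h agrees in direction: a placebo odds ratio of 2.0 appears as 1.54 after arm adjustment, with power of 36% against 51% for the placebo arm alone (43 per arm). A few sentences would also rule out the total to discharge, and the primary analysis would not move.

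Part of this stands. Below full blockade the single estimate is still biased as an estimate of the placebo-arm relation; power is not the only criterion. A careful analyst would show the association by arm with confidence intervals beside any overall figure, use an early or by-day dose, take no BM within 3 days as POI, and call the result an association.

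That is ordinary good practice, and the plan already permits it: allocation, BM times and daily doses are all collected. The case does not show that the plan prescribes something wrong. Naming the placebo-arm HR as the sole answer would also have a price. It rests on about 14–27 events and gives up power unless blockade is well beyond half. A 24-h landmark leaves out roughly 6–31 of 78 subjects, selected on an outcome that treatment affects.

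**Conclusion.** No change to the plan is needed. Section 5 leaves the method for an exploratory aim unwritten, and analysts can fill that gap sensibly from data already collected. Whether to give one slope or two is a fair trade-off. Two slopes protect against dilution if MNTX blocks most of the opioid effect, and one slope is more precise if it blocks less than about 60%. The documents do not say which case applies. The dilution ranges from none to an HR of 0.60 appearing as about 0.80, and every point in that range rests on an assumed effect size, dose distribution and degree of blockade. The timing concern falls away for the daily doses that the plan names. It would return only for a total to discharge combined with discharge that depends on BM. The log-rank comparison, the sample size of 86 and the randomized narcotics comparison are unaffected in every case.

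### Section 5 pre-specifies only a Fisher p-value for comparing safety between arms; it should report risk differences with 95% confidence intervals

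*Combined protocol and SAP*

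**What the plan says.** Section 5 (Statistical Analysis Plan) opens its safety paragraph with the data to be watched: "safety will be assessed by monitoring adverse events (AEs), concomitant medications, vital signs, physical examination findings, ECG findings, and laboratory test results". It adds that withdrawals because of adverse events are a safety end point. It then names the comparison: "Treatment-emergent AEs, potentially clinically important laboratory measurements" and "premature study discontinuations will be compared between groups by use of the Fisher exact probability test".

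No risk difference, ratio, confidence interval or margin is given for any safety measure, there or elsewhere in the document. No significance level, sidedness or power is given for the safety tests; the 0.05 level in Section 5 is attached to the secondary efficacy end points. The text does not say whether adverse events are compared term by term or as an overall any-event rate.

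The sample size in Section 3.2, repeated in Section 4.2, comes from efficacy alone: "A sample size of 43 randomly assigned patients per study group (86 subjects in total) was calculated to detect a treatment effect of MNTX", with "90% power; alpha = 0.05", on the assumption that "subjects who experience their first BM by day three comprise 50% in the placebo group and 85% in the treatment group". On attrition: "A 10% lost-to-follow up rate was also included in the calculation".

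**The concern.** A Fisher exact test on its own returns a p-value. It does not say how much more often an event occurred on MNTX, or how large an excess the data leave open. At 43 per arm, for events that are not common, a non-significant p-value is the likely result whether or not the drug raises the rate, so it carries little information about harm.

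This matters more here than in many small trials. The first dose is given before surgery, before any ileus exists (Section 4.3). Section 2.2 says the drug has not been studied as ileus prophylaxis after spinal fusion. Section 3.1 frames the aim as benefit without added narcotic use or a disturbed recovery. Readers will look to this trial for some measure of harm, and the plan as written commits to none.

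**Working it through.** **Inputs.** From the documents: 43 per arm, 86 in total, 10% loss (Section 3.2); Fisher exact test for safety (Section 5). Assumed, because the documents are silent: two-sided testing at 0.05 for safety, and every adverse event rate below.

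**1. The plan's own figure.** The 43 per arm can be approached from the bowel-movement rates alone. Under proportional hazards, 50% vs 85% with a first BM by day three gives a hazard ratio of ln(0.15)/ln(0.50) = 2.74. Freedman's log-rank formula, two-sided 0.05 and 90% power:

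- events = (1.960 + 1.282)² × ((1 + 2.74)/(1 − 2.74))² = 48.6, so 49
- per arm = 49/(0.50 + 0.85) = 36.3, so 37
- after 10% loss = 37/0.9 = 41.1, so 42

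That is one below the stated 43. A pooled two-proportion formula gives 36, or 40 after loss. The figure is thus explained by efficacy, with no safety input.

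**2. Chance that the Fisher test detects a true difference.** For each pair of true rates (p₁, p₂), sum Bin(i; 43, p₁) × Bin(j; 43, p₂) over all tables (i, j) whose two-sided Fisher p is at most 0.05.

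| Assumed rates | Power | Missed |
|---|---|---|
| 5% vs 10% | 5.1% | 95% |
| 10% vs 20% | 16.9% | 83% |
| 20% vs 40% | 44.9% | 55% |
| 10% vs 30% | 55.2% | 45% |
| 25% vs 50% | 60.8% | 39% |
| 30% vs 60% | 73.7% | 26% |

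With equal true rates, the test's actual two-sided error rate is 0.5% at a 5% event rate and 1.9% at 10%, so it is conservative for uncommon events.

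**3. Sensitivity for 10% vs 20%.** After the planned loss, 0.9 × 43 = 38.7 per arm. The miss rate is 84.5% at 39 per arm and 85.1% at 38. A one-sided Fisher test at 0.05 with 43 per arm has power 25.8%, so it misses 74%.

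**4. How much is due to the test and how much to the sample size.** Same rates, 43 per arm: the uncorrected chi-square test misses 74%, and a Newcombe 95% interval fails to exclude zero 76% of the time. Fisher misses 83%. Changing the method therefore recovers only 7 to 9 percentage points. About 199 per arm (219 with continuity correction) would be needed for 80% power.

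**5. What an interval adds.** Suppose 9/43 on MNTX (20.9%) and 4/43 on placebo (9.3%).

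- Fisher two-sided p = 0.23.
- Risk difference = 5/43 = 11.6 points.
- Wilson limits: MNTX 11.4% to 35.2%; placebo 3.7% to 21.6%.
- Newcombe lower limit = 0.1163 − √[(0.2093 − 0.1142)² + (0.2160 − 0.0930)²] = −0.039.
- Newcombe upper limit = 0.1163 + √[(0.3521 − 0.2093)² + (0.0930 − 0.0368)²] = +0.270.

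The p-value says only that the difference is not significant. The interval says that an excess of up to 27 points has not been ruled out. Even equal counts of 4/43 and 4/43 leave −13.5 to +13.5 points open.

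**The case against.** The strongest reply is that the plan contains no error. It states no safety hypothesis and no non-inferiority claim, and it nowhere says that a non-significant result will be read as safe. A reader might infer that it does, because a p-value is the only comparison named, but the text does not support that. The concessions about narcotic use and recovery in Section 3.1 also have their own outcomes: daily narcotics and time to discharge or discharge eligibility. All of this stands. The point is a missing estimate, not a contradiction.

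Second, small trials rarely have power for harms, and replacing Fisher would not change that. This also stands; step 4 of the working shows it. It would be wrong to read the 83% as the cost of choosing Fisher.

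Third, the result depends on the event rates chosen, and none are in the documents. A reader might conclude that any doubling or tripling of an adverse event would probably be missed. That is false for common events: 30% vs 60% is detected 74% of the time and 10% vs 30% 55%. If Section 5 means one overall any-event comparison, the rates could be high and the power better. The text allows either reading.

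Fourth, per-arm counts are needed for a Fisher test and will probably be tabulated, so a reader could compute the interval. That is likely, but it leaves the estimate and its interval outside the pre-specified analysis, and it leaves the p-value as the headline.

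Finally, Section 5 is just as brief on efficacy, naming no hazard ratio or interval for the primary end point. That puts the gap in proportion without removing it.

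**Conclusion.** The point holds as a cheap improvement to the analysis. Section 5 commits the trial to a between-arm safety p-value and to nothing that measures the size of harm or bounds it. For uncommon events at 43 per arm that p-value says little: 95%, 83% and 55% of true doublings from 5%, 10% and 20% would be missed, falling to 26% for a doubling from 30%. These figures rest on assumed event rates and an assumed two-sided 0.05 test; the one-sided version and the allowance for 10% loss leave the conclusion unchanged.

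Three stronger readings are not supported. The plan does not equate non-significance with safety. The low power comes mainly from the sample size and only in small part from the Fisher test. And a yes/no flag for potentially clinically important laboratory results is not wrong in itself: analysing Chem7 and CBC as continuous values adjusted for baseline answers a different question, and its advantage rests on shifts and correlations that the documents do not give. The primary efficacy result is unaffected.

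**What to change.** In Section 5:

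1. Make the primary safety presentation, for treatment-emergent adverse events, potentially clinically important laboratory results and premature discontinuations, the count and percentage per arm with the risk difference (MNTX minus placebo) and its 95% confidence interval, by the Newcombe or Miettinen-Nurminen method.
2. Keep the Fisher p-values as descriptive.
3. State that a non-significant p-value will not be reported as evidence of no difference between arms.

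It would also help to say whether adverse events are compared by term, overall, or both. Baseline-adjusted analysis of continuous laboratory values is optional and not part of this point.

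The cost is a few sentences and extra table columns, with no new data, patients or procedures. The downside is that the intervals will be wide, so the safety conclusion will read less favourably than a list of non-significant p-values. It will reflect more accurately what 43 patients per arm can show.
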